We have previously demonstrated in drug naïve youth with newly diagnosed type 2 diabetes that increased rates of gluconeogenesis are an important contributor to mild fasting hyperglycemia (glucose ~ 7 mmol/l)¹⁰. This finding contrasts with prior adult studies, in which high rates of gluconeogenesis were only observed in individuals with severe hyperglycemia (glucose > 8.5 mmol/l) and long-standing disease³¹. This early and severe dysregulation in gluconeogenesis is consistent with the aggressive nature of type 2 diabetes in youth³² and our preliminary results suggest that metformin may not be a potent first-line agent for this disease. **Preliminary Results:** In a pilot study of 5 multi-ethnic youth with newly diagnosed type 2 diabetes conducted at Baylor College of Medicine, we demonstrated that 3 months of metformin reduced HbA1c (6.8 ± 0.1 vs. $6.0 \pm 0.2\%$, $P < 0.01$) without a change in gluconeogenesis (1.78 ± 0.41 vs. $1.72 \pm 0.31 \text{ mg} \cdot \text{kg}^{-1} \text{min}^{-1}$, $P = \text{ns}$)³³. The participant characteristics for the pilot study conducted at Baylor were: 5 adolescent girls, age 13.7 ± 1.0 years; 3 African-American and 2 Hispanic. All individuals were maintained on metformin 1g twice daily x 12 weeks without side effects. The participants were instructed on basic education for diet and lifestyle at the start of the study, but there were no ongoing organized or supervised lifestyle regimens. Although not powered to detect weight loss, there was no significant detectable weight loss post metformin treatment. If attenuation of gluconeogenesis is not a primary driver of metformin's initial anti-hyperglycemic effect, metformin alone may be suboptimal in youth with type 2 diabetes. These preliminary results support a multi-mechanistic role of metformin and add credence to the mounting evidence that metformin may have pleiotropic effects.

Targeting incretin secretion with metformin

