- a) The change in the gut microbial composition and distribution in African-American youth with type 2 diabetes after 12 weeks of metformin.

Metformin response and pharmacokinetic-pharmacodynamic model

- b) Construct a pharmacokinetic-pharmacodynamic model based on plasma and RBC metformin concentrations, and treatment outcome response (including change in glucose production, gluconeogenesis, incretin concentrations).

Study Design and Methods

Study Design

This is a pilot randomized parallel design study of African-American youth with type 2 diabetes who are not on insulin therapy, with two intervention arms (combination therapy with metformin and liraglutide, and metformin alone).

Participants enter 5-7 day drug-free run-in period prior to initial metabolic evaluation. Participants will be evaluated before and after 12 weeks of study drug(s).

Randomization

The NIH Clinical Center (CC) Pharmacy will perform block randomization stratified by sex. Randomization will be stratified by sex with a block size of 6. The randomization schedules will be constructed by an independent statistician and shared with the NIH CC Pharmacy. The PI and study staff will not view the randomization schedule *a priori*. Subjects will be randomized as they enter the protocol as follows: The PI or study staff will notify the NIH CC pharmacy of the eligible enrolled participant and the pharmacy will assign the intervention arm according to the predetermined randomization schedule. All participant data will be entered into a NIDDK RedCap® database and the participant will be randomized consecutively using the single randomization list maintained by the NIH CC Pharmacy.

Study Protocol

Figure 1 illustrates the study design in which there will be 5 study visits: Visit 1 (screening outpatient), Visit 2 (tracer inpatient), Visit 3 and 4 (follow-up outpatient) and Visit 5 (tracer inpatient). Eligible patients may be identified at CNMC but no study visits will occur at CNMC.

[figure not shown]

Figure 1 –Study Design: randomized 12-week two-treatment arm clinical trial

Visit 1: Screening Outpatient Visit

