Individuals will be considered to be African-American if they self-identify as African-American and describe both parents as being African-American. In brief, African-American youth are disproportionately affected by type 2 diabetes and have lower treatment efficacy and higher morbidity rates compared to other ethnic groups. This project is designed to

investigate the underlying biological determinants (including genetic) in African-American youth with type 2 diabetes and provide information that will help to reduce the burden of disease in this vulnerable population.

Age Range 12- 25 years and pubertal status

The age range of 12- 25 years was chosen to maximize recruitment and includes a wide range of youth afflicted with type 2 diabetes. However, using a wide age range increases the potential to recruit youth across the pubertal spectrum and puberty is associated with changes in insulin resistance. Therefore, to minimize clinical variability, we will only recruit pubertal or post-pubertal youth (defined as Tanner stage IV-V for girls and testicular size 11-25cc for boys). We believe this approach is reasonable because we will have a well-defined cohort (by pubertal status) and a balanced distribution in intervention arm by sex (randomization stratified by sex). In addition, the primary outcome for this study (change in gluconeogenesis) varies minimally with age or pubertal status among pre-pubertal and pubertal youth^{10,77}.

Pubertal status will be defined based on breast examination (Tanner stage IV-V) in girls and testicular examination (11-25cc) in boys. Pubic hair and bone age will not be used to characterize pubertal stage.

Diabetes diagnosis criteria and HbA1c <9%

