Sample size estimates are based on the mean changes and standard deviations observed in our pilot study (Table 2). Assuming a two-sided alpha of 0.05 and standard deviations of change from baseline of $0.20 \text{ mg} \bullet \text{kg}_{\text{lbm}} \bullet \text{min}$ for gluconeogenesis and $0.50 \text{ mg} \bullet \text{kg}_{\text{lbm}} \bullet \text{min}$ for glucose production, a trial with 12 participants in each group will have 80% power to detect a difference between metformin and combination therapy of $0.24 \text{ mg} \bullet \text{kg}_{\text{lbm}} \bullet \text{min}$ in gluconeogenesis and in $0.60 \text{ mg} \bullet \text{kg}_{\text{lbm}} \bullet \text{min}$ in glucose production. Analyses within each group will have 80% power to detect a change from zero if the true change is ≥ 0.18 and $\geq 0.44 \text{ mg} \bullet \text{kg}_{\text{lbm}} \bullet \text{min}$ for gluconeogenesis and glucose production respectively. For

the secondary outcome of change in GLP-1 AUC after an OGTT, we will have $> 95\%$ power to detect the mean difference of 101 pg•min/ml. **Assuming a 25% attrition rate, we will recruit 16 in each group.**

Table 2: Mean and Estimated Rates of Gluconeogenesis and Glucose Production and Projected Effect Sizes*

	Baseline Mean (SD)	Follow-up Mean (SD)	Difference Mean (SD)	15% Decrease	20% Decrease
Gluconeogenesis (mg•kg _{lbm} •min)	1.78 (0.41)	1.73 (0.31)	0.05 (0.19)	0.27	0.36
Glucose Production (mg•kg _{lbm} •min)	2.93 (0.92)	2.67 (0.54)	0.27 (0.50)	0.44	0.59
Early intact GLP-1 AUC (pg•min/min)	137 (113)	238 (128)	101 (32)	-	-

*Data from pilot study in 5 youth with type 2 diabetes treated with metformin 1000mg twice daily for 3 months.

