This power analysis was performed with two-sided T tests to detect a between group difference of a 15% change in gluconeogenesis which would require 12 individuals per group. Our primary assumption is that there will be a 15% difference in gluconeogenesis between the two study arms. This assumption is underscored by the fact that metformin will not result in a change in gluconeogenesis *in vivo*^{24,26,27} but liraglutide will decrease rates of gluconeogenesis by 15%. This sample size is in keeping with previous studies assessing metformin effect using similar techniques to measure of gluconeogenesis^{24,25}. Nevertheless, we acknowledge that the delta difference and SD for change between two differently treated groups could be larger. Therefore, this pilot study will provide valuable preliminary information for the magnitude of the difference between intervention groups that would be crucial for a larger randomized placebo controlled trial.

Analysis of Primary and Secondary Outcomes

The primary outcome, the change in gluconeogenesis from baseline to 12 weeks, will be analyzed using an analysis of variance that compares the two randomized groups adjusting for baseline levels. Similar analyses will be performed for the secondary outcomes, using transformations or nonparametric tests as appropriate. Secondary regression analyses will adjust for the effect of other variables (such as fat mass, metabolite and hormonal concentrations etc.) on these changes.

Analysis of Exploratory Outcomes

Pharmacogenomic Variants of Metformin Response

Given the limited sample size, the proposed genetic aims are exploratory in nature. First we will use 9 previously-identified genetic variants (Table 1) to construct a genetic risk score, calculated as the sum of the risk alleles that the individual has for any of the variants. Metformin response will be assigned as a 15% change in gluconeogenesis from baseline (minimum clinically relevant effect size) for each individual^{26,91}. We will then compare this risk score in the metformin responders vs. non-responders. The genetic risk score based on these 9 variants associated with metformin response in adults will be analyzed as a single predictor, and not by individual variants. Since this approach may miss important variation in these genes, particularly given that the question of metformin response has been less well studied among African-Americans, we will also sequence the genes of interest in these individuals.

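### The primary model omits sex, the randomisation stratum, and loses power if sex predicts change in gluconeogenesis; the primary outcome also names no metabolic state

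*Combined protocol and SAP*

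**What the plan says.** Under Randomization the protocol states: "Randomization will be stratified by sex with a block size of 6". The rationale for the age range relies on this stratification for "a balanced distribution in intervention arm by sex (randomization stratified by sex").

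Under Analysis of Primary and Secondary Outcomes, the change in gluconeogenesis to 12 weeks "will be analyzed using an analysis of variance that compares the two randomized groups adjusting for baseline levels". No other covariate is named for the primary test. A later sentence adds: "Secondary regression analyses will adjust for the effect of other variables (such as fat mass, metabolite and hormonal concentrations etc". That list is open and so does not exclude sex, but it governs secondary regressions only.

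The sample-size section says that "a trial with 12 participants in each group will have 80% power" for a difference of 0.24 with an SD of change of 0.20 (mg per kg lean mass per minute), and then: "Assuming a 25% attrition rate, we will recruit 16 in each group". The SD comes from the pilot, whose participants were "5 adolescent girls" (Background, Preliminary Results).

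On the secondary point, neither the primary outcome under Study Objectives, nor the gluconeogenesis row of Table 2, nor the analysis section names a metabolic state. Aim 1 and its hypothesis cover both the overnight fast and meal absorption, and each tracer visit samples a fasting and a fed steady state.

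**The concern.** Stratifying by sex keeps the arms close to balanced on sex, so the true variance of the arm comparison contains little between-sex variation. A model without sex still counts that variation as residual error. If sex predicts change after baseline is accounted for, the reported standard error is too large, the confidence interval too wide and the type I error below 5%. Power is lost with no protection gained in return.

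The planning SD makes this more relevant. It was estimated in girls only, while the trial enrols both sexes, so a real sex difference would add variance that the power calculation did not include. The plan also says "this pilot study will provide valuable preliminary information for the magnitude of the difference between intervention groups" for use in designing a larger trial, so the width of the interval matters as well as the p-value.

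On the unnamed state, two measured quantities fit the definition of the primary outcome. The one that decides the trial could be chosen after the data are seen. If both must succeed, as the Aim 1 hypothesis could be read, the power is lower than that planned for a single variable.

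**Working it through.** **1. The plan's own figure.** Unadjusted two-sample t test, two-sided 0.05, 12 per arm: effect size 0.24/0.20 = 1.2, noncentrality 1.2 × √(12/2) = 2.94, 22 df. Power is 80.2% and the required n is 11.94, so 12 per arm. Attrition: 12/(1 − 0.25) = 16. The stated figures reproduce.

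**2. Cost of the extra term alone.** With 12 per arm and SD 0.20, noncentral t power is 80.0% with 21 df (arm + baseline) and 79.8% with 20 df (arm + baseline + sex).

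**3. Effect on the SD.** If the sexes differ by d in change and a share p is female, the SD without sex is √(0.20² + p(1 − p)d²). At p = 0.6 this is 0.206, 0.223 and 0.248 for d = 0.1, 0.2 and 0.3.

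**4. Simulation** (100,000 trials per cell). From the documents: 32 randomised in blocks of 6 within sex, 24 completers, arm difference 0.24 (or 0 for type I error), baseline SD 0.41. Assumed: 60% female, within-sex SD 0.20, random dropout, baseline uncorrelated with change, and the values of d. A d of 0.3 exceeds the treatment effect and is an upper bound.

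| d | Power without sex | Power with sex | Mean SE ratio, without/with | Type I error without sex |
|---|---|---|---|---|
| 0 | 77.5% | 76.6% | 0.99 | about 5% |
| 0.1 | 75.5% | 76.7% | 1.02 | 4.6% |
| 0.2 | 69.5% | 76.8% | 1.11 | 3.6% |
| 0.3 | 59.8% | 76.7% | 1.24 | 2.7% |

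Type I error with sex in the model stays at about 5.0%. The starting level of about 77% rather than 80% reflects unequal arms after random dropout and lost degrees of freedom, not sex.

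**5. Break-even.** At d = 0.06 power is 77.1% without sex and 76.9% with it; at 0.07 it is 76.7% and 76.8%. Break-even is therefore near 0.065, about a third of the SD.

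**6. Sensitivity**, for d = 0.1 / 0.2 / 0.3:
- 75% female: 76.1 / 71.3 / 63.4% without sex, 76.6% with it.
- 0.20 taken as the total SD, so within-sex SD = √(0.04 − 0.24d²): 78.0 / 79.3 / 82.0% without sex, 79.2 / 87.1 / 97.6% with it.
- Baseline correlated with change. Table 2 implies cov(baseline, follow-up) = (0.41² + 0.31² − 0.19²)/2 = 0.114, so the correlation of change with baseline is (0.114 − 0.168)/(0.19 × 0.41) = −0.69. This rests on five participants and is very imprecise. Power is then 95.1 / 89.8 / 79.0% without sex, about 96% with it.

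**7. Metabolic state.** Suppose each state's test has 80% power. Power to win on both is 0.80² = 64% if the states are independent, and 69% and 75% at correlations of 0.5 and 0.9. For 80% on both, each test needs 89.4 / 87.9 / 84.3% power, which is 15.3 / 14.6 / 13.3 per arm, or 16 / 15 / 14 completers instead of 12. If either state could carry the claim at 0.05, a rule the plan does not state, family-wise error would be about 7% at correlation 0.9 and up to 1 − 0.95² = 9.75% if independent.

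**The case against.** The primary test as written is valid: no bias and no inflated alpha. The loss depends on a sex effect that the documents do not report. At d = 0.1 the gain is only about 0.5 to 1.2 points, below 0.065 there is none, and the large losses need sex differences of 1.0 to 1.5 within-sex SDs. All of that stands, which is why no single figure can be given.

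The strongest objection is that baseline adjustment may already absorb a sex effect; scaling rates to lean mass may do so too. If the sex difference acts wholly through the baseline level, then at a change–baseline correlation of −0.4 power is 84.7% without sex and 83.4% with it, and at −0.69 it is 96.2% against about 95.8%. This is correct, and it means the concern applies only to a sex effect on change beyond baseline. It does not defeat the fix, because the loss from adding sex is again only about 1 point.

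Uncertainty in the pilot SD is also larger than anything sex would add. With n = 5, the 95% interval runs from √(4 × 0.19²/11.14) = 0.11 to √(4 × 0.19²/0.484) = 0.55, and the plan concedes that the SD could be larger. That is a separate problem and no reason to leave avoidable variance in the error term.

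The unnamed state could be ranked first, since it leaves the endpoint open. The 64 to 75% range also assumes 80% power for each state, whereas Table 2 has a single unlabelled row. Both remarks are fair; nothing in the documents settles which state decides.

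**Conclusion.** The concern holds. Sex is the stratification factor, and it is absent from the primary model. If it predicts change beyond baseline, the test is conservative and underpowered. Under the base assumptions the loss relative to a model with sex is about 1 point at a sex difference of 0.1, 7 points at 0.2 and 17 points at the upper bound of 0.3. If sex adds nothing beyond baseline, including it costs about 1 point. The sign of the net effect therefore depends on a quantity the documents do not give, but the possible gain is much larger than the possible cost. This should be changed; confidence is medium because the sex effect is unknown.

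The secondary point rests on the text alone: the metabolic state that defines the primary outcome is not specified.

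**What to change.** Write the primary model as change = arm + baseline value + sex, and use the same covariates for secondary outcomes analysed by a linear model. Before any analysis, name one metabolic state as primary, at the sponsor's choice, and report the other as secondary. If both are required, say so and restate the power for that rule.

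This takes two or three sentences in the objectives and the statistical section. Adding sex and naming one state leave the design, sample size and data collection unchanged: sex is already known at randomisation and both states are already measured. Sex uses one degree of freedom. The price of naming one state is that the other can no longer carry the primary claim.

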We will use regression models to determine if this risk score predicts metformin response in terms of changes in rates of gluconeogenesis and metformin concentrations in serum and urine, after adjustment for genome-wide proportion of African ancestry (additional covariates will be evaluated for inclusion), with $p < 0.05$ considered statistically significant. Rare variants identified during targeted gene sequencing will be analyzed in a composite way, collapsed by gene and considered with a rare variant analysis tool (e.g. SKAT⁹²). While this analysis may have limited power, the identification

of additional variants in these genes among African-American youth will inform future larger studies. Additionally, we will determine whether adding the sum of the risk alleles as covariates modifies the statistical analyses for the outcomes in Aim 1 and Aim 2. The composite genetic risk score will be used to adjust the primary outcome analysis of change in gluconeogenesis to see if accounting for this variation influences our conclusions. These results will be evaluated using a likelihood ratio test comparing a regression model adjusted and unadjusted for the variant.

Gut Microbiome and Metformin

Statistical analysis will be performed using a variety of computer packages including XLstat, NCSS 2007, “R” and NCSS 2010. Alpha and beta diversity analysis will be conducted as previously described^{86-88,93} using Qiime (www.qiime.org). Significance reported for any analysis is defined as p<0.05.

Metformin Pharmacokinetics

Statistical analysis and non-linear mixed effect modeling will be performed using the “Phoenix WinNonlin”, an industry standard for non-compartmental analysis, pharmacokinetic/ pharmacodynamic modeling.

Multiple-site Studies

Eligible patients may be identified through CNMC but no enrollment, informed consent or study visits will occur at CNMC.

The primary IRB on record will be NIH IRB. A Federalwide Assurance for Human Subject’s Protection (FWA) for Children’s National Medical Center is FWA00004487 and for PBRC is FWA 00006218.

We will also utilize the Translational Research in Pediatrics Program (TRIPP), an established contractual agreement between CNMC and the National Institutes of Health Clinical Center (NIH CC). A Reliance agreement has been executed between NIH and CNMC.

Human Subject Protection

Informed Consent/Assent Procedures

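### The metformin-responder rule pools both arms, so at the plan's own planning values about 85% of those it labels would be on liraglutide (minor; exploratory aim only)

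*Combined protocol and SAP*

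**What the plan says.** The rule is in Analysis of Exploratory Outcomes, under Pharmacogenomic Variants of Metformin Response: "Metformin response will be assigned as a 15% change in gluconeogenesis from baseline (minimum clinically relevant effect size) for each individual". The next step is: "We will then compare this risk score in the metformin responders vs. non-responders". Neither sentence names an arm or a direction. Under Pharmacogenomic Analysis of Metformin, all participants are genotyped, and the Précis allocates 16 to metformin plus liraglutide and 16 to metformin alone.

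Sample Size Justification – Primary Study assumes that "metformin will not result in a change in gluconeogenesis" and that "liraglutide will decrease rates of gluconeogenesis by 15" percent. It adds that "we acknowledge that the delta difference and SD for change between two differently treated groups could be larger".

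The pharmacogenomic section also plans two continuous analyses:

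- A regression of change in gluconeogenesis (and of metformin concentrations) on the score, "after adjustment for genome-wide proportion of African ancestry (additional covariates will be evaluated for inclusion"). Arm is not named.
- A step in which "The composite genetic risk score will be used to adjust the primary outcome analysis of change in gluconeogenesis", evaluated by a likelihood ratio test. The primary analysis is "an analysis of variance that compares the two randomized groups adjusting for baseline levels", so this second model contains arm and baseline.

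**The concern.** A phenotype called metformin response should reflect what metformin did. In the combination arm, a fall in gluconeogenesis is the joint result of two drugs, and the rule cannot separate them. On the plan's own assumptions the metformin part is zero and the liraglutide part equals the cut-off. A pooled label would therefore mark mainly who was allocated liraglutide, plus random variation.

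The pilot is meant to inform later work, and its genomic and phenotype data are to be shared. A reader or later user of a pooled responder table would take it to describe metformin, and under the planning assumptions it would not. A secondary cost is precision: a score analysis without arm leaves the between-arm difference in the residual variance.

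**Working it through.** **Inputs.** From Sample Size Justification and Table 2: baseline gluconeogenesis 1.78 (SD 0.41); planning SD of change 0.20 (pilot 0.19, five participants on metformin); assumed mean change 0 on metformin alone and −15% on the combination; 12 completers per arm. Assumptions added here: normally distributed changes, the same SD in both arms, equal attrition, and pooling of the arms.

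**The plan's own figure.** A two-sample t test with 12 per group, difference 0.24, SD 0.20 and two-sided alpha 0.05 has power 0.802, and 12 / 0.75 = 16 recruited per group. Both agree with the plan.

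**Threshold.** 0.15 × 1.78 = 0.267. This is also the assumed mean fall in the combination arm.

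**Decreases only.**

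- Metformin alone: Φ(−0.267 / 0.20) = Φ(−1.335) = 0.091, or 12 × 0.091 = 1.1 participants.
- Combination: Φ(0) = 0.500, or 6.0 participants.
- Share of those labelled who are on liraglutide: 0.500 / (0.500 + 0.091) = 0.846.

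**Either direction.**

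- Metformin alone: 2 × 0.091 = 0.182, or 2.2 participants.
- Combination: 0.500 + Φ(−0.534 / 0.20) = 0.500 + 0.004 = 0.504, or 6.0 participants.
- Share: 0.504 / (0.504 + 0.182) = 0.735.

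If the label were unrelated to arm, the share would be 50%.

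**Sensitivity of the liraglutide share.**

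| Change to inputs | Decreases only | Either direction |
|---|---|---|
| Planning values | 85% | 73% |
| Combination mean −0.24 (the powered difference) | 83% | 71% |
| SD 0.19 (pilot) | 86% | 76% |
| Metformin-alone mean −0.05 (pilot) | 78–81% | 72–75% |
| Threshold taken on each person's own baseline | 83–91% | 71–74% |
| SD 0.30 (assumed) | 73% | 59% |
| SD 0.40 (assumed) | 66% | 54% |

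The last two rows matter because the plan itself allows for a larger SD.

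**How far arm determines the label.** The squared correlation between arm and label is (difference in rates)² / 4, divided by p(1 − p), where p is the average rate. Decreases only: (0.409² / 4) / (0.2955 × 0.7045) = 0.20. Either direction: (0.322² / 4) / (0.343 × 0.657) = 0.12.

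**Precision lost by omitting arm from the continuous regression.** With 24 completers and an arm difference of 0.267, the variance of change around a single mean is about SD² + (24/23)(0.267/2)². The score has 23 degrees of freedom of spread without arm and 22 within arms. The ratio of slope standard errors, without arm to with arm, is therefore about √{[1 + (24/23)(0.1335/SD)²] × 22/23}:

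- SD 0.20: √(1.465 × 0.957) = 1.18
- SD 0.30: √(1.207 × 0.957) = 1.07
- SD 0.40: √(1.116 × 0.957) = 1.03

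**Validity.** Randomisation makes the score independent of arm in expectation, so omitting arm does not bias the score comparison. A simulation with 12 per arm and nine variants, taken as independent at the Table 1 frequencies, gave type I error of 4.6% to 5.3% for t tests.

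**The case against.** The strongest reply is that much of the remedy is already in the plan. Change in gluconeogenesis is also regressed on the score as a continuous outcome, further covariates are left open, and the score is added to the primary model, which has arm and baseline. This stands in large part. What remains is that arm is not prespecified in the regression that tests the score. The step that does include arm is framed as a check on the treatment conclusion, and neither changes the responder comparison.

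A second reply is that a decrease is plainly meant: the threshold is called a minimum clinically relevant effect and Table 2 projects decreases. This also stands, so the missing sign is a drafting omission and 85% is the more natural figure. That reading raises the liraglutide share.

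Third, the plan names no test for the responder comparison and calls the genetic aims exploratory. That is fair, and it limits the point to labelling and precision.

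Three stronger readings are tempting, and the documents support none of them:

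- *Liraglutide caused 85% of the responses.* The share counts who is labelled. The excess over the metformin-alone rate is (0.500 − 0.091) / 0.591 = 69% of those labelled.
- *The gene–response association is confounded by arm, or false positives are inflated.* Randomisation rules this out in expectation. Chance imbalance in so small a trial is possible, and adjusting for arm deals with it.
- *The primary result is affected.* The primary analysis does not use the rule.

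**Conclusion.** The point holds as a minor one, confined to an exploratory aim. The responder rule as written pools two arms that the plan expects to differ by exactly the responder threshold. At the planning values about 85% of those labelled as responders by a decrease would be on liraglutide. The share is 73% if either direction counts, and 66–73% for decreases at assumed SDs of 0.40 to 0.30. The comparison is not invalid; the phenotype carries the wrong name, and precision is lost if arm is left out. That loss is real at SD 0.20 (slope standard error about 18% larger) and small near SD 0.40 (about 3%).

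The conclusion rests on pooling, which is inferred from the rule applying to each individual and from genotyping everyone, since no section limits it to one arm. It also rests on normal changes with a common SD and on the plan's assumed arm means. The documents give no per-allele effect, so no power figure for the score is offered.

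**What to change.** Make the model the plan already comes close to the main risk-score analysis for gluconeogenesis: continuous change from baseline to 12 weeks on risk score, randomised arm, baseline gluconeogenesis and genome-wide African ancestry. Report the score coefficient with its 95% confidence interval.

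Keep any responder table as descriptive only. Define response as a decrease of at least 15% from the participant's own baseline, show it separately by arm, and do not call it metformin response in the combination arm.

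The cost is a change of wording. Arm and baseline are already collected and already in the primary model. Relative to the ancestry-only regression they use two more degrees of freedom, leaving 24 − 5 = 19 residual degrees of freedom instead of 21 with about 24 completers. If the SD of change proves nearer 0.40, the precision gained from naming arm will be slight, but the labelling correction is still needed.

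### The genetic-score regression on change in gluconeogenesis fixes only African ancestry as a covariate; naming baseline gluconeogenesis too would be a nearly free gain in precision and prespecification

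*Combined protocol and SAP*

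**What the plan says.** Three places in the combined protocol and SAP bear on the point.

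- **Analysis of Exploratory Outcomes, Pharmacogenomic Variants of Metformin Response.** Regression models are to "determine if this risk score predicts metformin response in terms of changes in rates of gluconeogenesis", and also in terms of metformin concentrations. Genome-wide African ancestry is the one fixed covariate. Other covariates are to be considered for entry, with no list, rule or timing, and p<0.05 is the threshold. The same section also plans to add the composite score to the primary analysis and to compare the models with and without it by a likelihood ratio test. It further plans a comparison of the score between responders and non-responders, defined by a 15% change from baseline, and names no covariates for it.
- **Analysis of Primary and Secondary Outcomes.** The 12-week change in gluconeogenesis, as the primary endpoint, "will be analyzed using an analysis of variance that compares the two randomized groups adjusting for baseline levels".
- **Sample Size Justification – Primary Study, Table 2.** Gluconeogenesis has SD 0.41 at baseline, 0.31 at follow-up and 0.19 for the difference. The footnote gives the source: "Data from pilot study in 5 youth with type 2 diabetes treated with metformin 1000mg twice daily for 3 months".

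The plan calls the genetic aims exploratory because the sample is small.

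**The concern.** The same outcome is modelled twice, with baseline fixed in one model and left open in the other, and no reason is given. A change score contains the baseline value with a minus sign, so baseline is often a useful predictor of change. Where it is, leaving it out puts that variation into the residual and widens the standard error of the score's slope. With about 24 evaluable participants, precision is scarce.

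The open covariate list is the second half of the point. It allows several models with different p-values and does not say which one is reported. The likelihood ratio test does not settle this. Its purpose is to see whether the score alters the treatment comparison, and it does not name ancestry, which the section Pharmacogenomic Analysis of Metformin calls important in an admixed population. The result is two tests of one score on one outcome, with different covariates and no order of precedence.

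**Working it through.** **The plan's own figure.** The plan states no power or R² for the score regression. The nearest figure is for the primary comparison: "a trial with 12 participants in each group will have 80% power to detect" a difference of 0.24 with SD of change 0.20 and two-sided alpha 0.05. A two-sample t test using the noncentral t distribution gives 80.2%, so the figure reproduces. Attrition also agrees: 12 / (1 - 0.25) = 16 per group, or 32 recruited and 24 evaluable.

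**How much of the change baseline explains (Table 2).** Take change as follow-up minus baseline, with SDs 0.41, 0.31 and 0.19.

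1. cov(baseline, follow-up) = (0.41² + 0.31² - 0.19²) / 2 = (0.1681 + 0.0961 - 0.0361) / 2 = 0.1141.
2. r(baseline, follow-up) = 0.1141 / (0.41 × 0.31) = 0.90.
3. r(change, baseline) = (0.1141 - 0.1681) / (0.19 × 0.41) = -0.69.
4. R² = 0.48. The planning SD of 0.20 gives 0.47. Rounding of the three SDs alone allows 0.42 to 0.55.

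**What adjustment would gain at that R².** The residual SD is multiplied by √(1 - 0.48) = 0.72, so 0.20 becomes 0.144. The standard error falls by about 28%, which is worth 1 / (1 - 0.48) ≈ 1.9 times the sample size.

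The table gives the slope per SD of score detectable with 80% power, two-sided 5%. The noncentrality is slope × √(N - 1) / residual SD. Ancestry is in both models and one degree of freedom is charged for baseline. The score is assumed uncorrelated with the other covariates, and ancestry is given no explanatory power.

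| N analysed | Without baseline | With baseline |
|---|---|---|
| 24 | 0.123 | 0.088 |
| 32 | 0.104 | 0.075 |

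Both rows pool the two arms, which the plan does not state. Charging a further degree of freedom for arm changes these figures by less than 0.001.

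**How uncertain the 48% is.**

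- With n = 5, Fisher's z for r = -0.69 is -0.855 ± 1.96/√2. The approximate 95% CI for r is -0.98 to +0.49 (p = 0.19). Adjusted R² = 1 - 0.519 × 4/3 = 0.31.
- Much of the correlation comes from the SD falling from 0.41 to 0.31. With the same r of 0.897 and equal SDs, r(change, baseline) = -√((1 - 0.897)/2) = -0.23. R² is then about 0.05 and the gain about 1.05 times the sample size.
- A Pitman–Morgan test of the fall in SD gives r = 0.072 / (0.702 × 0.19) = 0.54, t = 1.11 on 3 df, p about 0.35. The fall is compatible with chance.
- At an intermediate R² of 0.2, the standard error is multiplied by 0.89 (1.25 times the sample size).

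**Cost if baseline explains nothing.** At N = 24 the residual degrees of freedom go from 21 to 20. The standard error rises by about √(21/20) - 1 = 2.5%.

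**The case against.** The strongest reply has four parts.

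1. **The plan does not exclude baseline.** The covariate list is open, so a reader who infers that baseline is left out goes beyond the text. This stands. The gap is that baseline is not prespecified.
2. **A baseline-adjusted test of the score is already planned.** Read with the primary analysis section, the likelihood ratio test compares models that contain baseline and arm. This also stands, and nobody should conclude that no such analysis exists. It does not close the gap, because that analysis does not name ancestry and serves a different purpose.
3. **Five participants cannot support a claim that baseline explains half the variance.** This stands. The 48% is a point estimate whose interval includes zero, from metformin alone, and the benefit may be negligible.
4. **Adjustment is not plainly a correction.** A reader might infer that, without baseline, regression to the mean could pass for a genetic effect. The documents do not support that. A chance link between score and baseline is already reflected in the unadjusted standard error, so the false-positive rate is not raised. Genotype is not randomised, and the protocol expects most participants to have been on metformin before a washout of 5 to 7 days. A real link between score and baseline is therefore possible, and adjusting for an error-prone baseline could then shift the score's coefficient. This supports showing the fit without baseline beside the adjusted one; it is no reason to leave the choice open.

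The exploratory status of the aim limits how much any of this matters.

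**Conclusion.** The point holds as a free improvement of low severity. The score regression on change in gluconeogenesis fixes ancestry but not baseline, the primary model of the same outcome fixes baseline, and no stated analysis of the score names both.

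The benefit of adjustment lies between roughly nothing and, at the Table 2 point estimate, a standard error about 28% smaller. The cost if baseline is uninformative is about 2.5% in standard error at N = 24. That imbalance justifies the change even though the size of the gain is poorly known.

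The upper figure assumes that the pilot SDs carry over to this trial, that the same relation holds in both arms, and that score and baseline are uncorrelated. The primary analysis is unaffected.

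**What to change.** Add one sentence to the pharmacogenomic analysis section: the regression of change in gluconeogenesis on the genetic risk score will include the baseline value of the same gluconeogenesis measure and genome-wide African ancestry as prespecified covariates, and models with any further covariates will be reported as sensitivity analyses. The fit without baseline can be listed among those. It would help to say in the same place that this regression, not the likelihood ratio test, is the main analysis of the score against change in gluconeogenesis.

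The cost is one sentence and one degree of freedom. Baseline gluconeogenesis is already measured at Visit 2, so no data, visits or participants are added.
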